11. ANALYSIS

11.1. Data Analysis

Patients will be classified based on their ages, emergency medicine diagnosis and early warning scores.

The normality analyses of the data will be performed using the Kolmogorov-Smirnov and Shapiro-Wilk tests. The data did not comply with normal distribution. The continuous variables will be expressed as the median (inter-quartile range), and the categorical variables were expressed as a number (percentage). The inter-group differences between the continuous variables will be evaluated using the Kruskal-Wallis test and the Mann-Whitney U test (with Bonferroni correction). The inter-group differences between the categorical variables will be evaluated using the Chi-square and Fischer Exact tests. The predictive power of the scores for hospitalization and mortality in hospital will be evaluated using the Receiver Operating Characteristic (ROC) analysis. The values of the Areas Under the ROC Curve (AUC) will be evaluated. The optimum cut-off points of the scores will be determined for both of the main endpoints using the Youden index (sensitivity+specificity-1).

Using these determined cut off points for the sensitivity, specificity, positive predictive value, negative predictive value, likelihood ratio (+) and likelihood ratio (-), the values of both the scores will be calculated for both hospitalization and mortality at the hospital. Graph representation will be used to increase understanding of data.

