Previously the TEDGeS (Turkish Emergency Departments Geriatric Scoring Study) pilot study was carried out and published (15,16). This study enrolled all geriatric patients (age ≥ 65 years) and carried out in 13 centers (University Hospitals, Government Education and Research Hospitals and Military Hospital ED) from different cities of Turkey.

Key findings were:

- Overall 30 % of hospitalized patients from ED are elderly patients and 30 % of these hospitalized patients were ICU hospitalizations
- In hospital mortality rate is about 6 % which is very high for general hospitalized patients
- The most common presenting symptoms are related to gastrointestinal systems and about 80 % of the cases using at least one chronic medication (22.2 % of the cases using more than 4 chronic medications)
- About 45 % of the cases final diagnosis are related to cardiovascular system and gastrointestinal system and nearly 85 % of the hospitalized cases are treated in non-surgical clinics (cardiology-pulmonology-internal medicine 65 %)
- MEWS, VIEWS and REMS scores are significantly high in hospitalized patients compared to discharged from ED and also these three scores are high in ICU hospitalized patients compared to both ward hospitalized and discharged patients.

- MEWS, VIEWS and REMS scores are significantly high in non-survivors compared to survivors.
- MEWS, VIEWS scores has higher sensitivity and specificity in terms of in-hospital mortality

These results suggest that geriatric patients not only constitute significant proportion of ED presentations but also they need more hospitalization. The predictive powers of the MEWS, VIEWS and REMS scores for hospitalization and mortality in geriatric patients those presented to ED are significantly high and might be concerned in the ED triage of these patients.

References

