3.2. Study objectives

MAIN OBJETIVE

The main objective of this project will be

- To determine Epidemiologic and Age Related Characteristics of Geriatric Patients presenting to the ED across Europe.

SECONDARY OBJETIVES

- To evaluate Early Warning Scoring systems (REMS, MEWS and VIEWS Scores) and determine most suitable Geriatric Emergency Medicine Risk Score regarding hospitalization, ICU admission and in-hospital mortality for patients
- To determine the most effective triage elements that can be used to predict hospitalization of geriatric patients presented to ED

- To determine the in hospital mortality and short term mortality rates of the patients above 65 years of age presenting to the ED across Europe.
- Sub analysis of ED discharged patients versus admitted patients for characteristics, comparison to recommended care and re-ED visit.
- Comparison of European data characteristics, investigation, treatment and outcome to similar data in other part of the world.

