11.3.1. Sample size

As this is a descriptive study, a formal sample size calculation has not been performed.

Based on our past experience of similar studies, we would expect to enroll between 40 and 50 sites each with an average number of patients of at least 25/site per 7 days study period.

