 Patient Has Home Care Service  Yes  No  Patient Has History of Falls  Yes  No  Patient Has Temporary Disorientation  Yes  No  Discharged From the Emergency Department Length of stay in ED:         (hours)  Admission to the Emergency Observation unit Length of stay in Obser. Unit:         (hours)  Admitted to Wards  Cardiology  Pneumology  Internal Medicine  Geriatrics  General Surgery  Neurosurgery  Orthopedics/Traumatology  Thorax Surgery  Cardiovascular Surgery  Other  Admitted to Intensive Care Unit  Death at ED  Death during Hospitalization	
For HOSPITALIZED PATIENTS
 
STATUS at 30 days:
 
30 days:  Alive  Death
 
If Admitted to Wards or ICU
 
 Total Length of Stay in Hospital:    (days)
 
 Total Length of Stay in Wards:    (days)
 
 Total Length of Stay in ICU:    (days)
 
 Still in Wards
 
 Still in ICU

Appendix 2

Country questionnaire

Number of ED proposed

Emergency Department Questionnaire

Institution:

Address:

Local PI:

Last name: _____ First name: _____

Phone: _____

e-mail address:

How many patients per year do you receive in your Emergency Department (ED) _____

How many patients per year do you hospitalize either in your hospital or in another hospital: _____

Total number of patients presented to your ED during the study week _____

Population served (habitants) by your ED _____

Is your ED located in a: **(check ONLY ONE BOX)**

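### Section 11.1 gives Europe-wide proportions, medians and AUCs no measure of precision and ignores clustering by ED and country; separately, the 30-day mortality objective and the CRF cover different patients.

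*Combined protocol and SAP*

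**What the plan says.** The main objective in Section 3.2 is "To determine Epidemiologic and Age Related Characteristics of Geriatric Patients presenting to the ED across Europe". A secondary objective asks for the "in hospital mortality and short term mortality rates of the patients above 65 years of age presenting to the ED across Europe". Section 5.6 requires each centre to enrol all consecutive cases, Section 10.1 has one national coordinator per country select the centres, and Section 11.3.1 expects "between 40 and 50 sites each with an average number of patients of at least 25/site".

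Section 11.1 is the whole analysis plan. Its summaries are: "The continuous variables will be expressed as the median (inter-quartile range), and the categorical variables were expressed as a number (percentage"). Continuous variables are compared by Kruskal-Wallis and Mann-Whitney tests. For the rest: "The inter-group differences between the categorical variables will be evaluated using the Chi-square and Fischer Exact tests". For the scores: "The predictive power of the scores for hospitalization and mortality in hospital will be evaluated using the Receiver Operating Characteristic (ROC) analysis". AUC values and Youden cut-offs follow. No confidence interval is named anywhere, and neither site nor country enters any analysis.

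On mortality, Section 13 of the synopsis lists 30-day status without restriction. In the CRF (Appendix 1), 30-day status stands under the heading "For HOSPITALIZED PATIENTS", and death at the ED and death during hospitalization have separate boxes.

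**The concern.** An inter-quartile range shows how patients differ from each other, not how precisely a median is known, and a bare percentage shows no precision at all. Section 11.3.1 omits a sample size calculation because the study is descriptive, so precision is stated nowhere, before or after the data.

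Patients in one ED share a catchment, a case mix and admission habits, and EDs in one country share a health system. An interval added later with the usual independent-patient formula would be too narrow for an overall rate if any such correlation exists.

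The mortality problem is of another kind. If 30-day status is recorded only for admitted patients, the rate named in Section 3.2 cannot be calculated, whatever Section 11.1 says.

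**Working it through.** The plan states no precision, power or ICC, so there is no figure to reproduce. Section 11.3.1 implies 40 × 25 = 1,000 to 50 × 25 = 1,250 patients as a minimum. Every ICC, the admitted share, the spread of site sizes and the number of countries below are assumptions.

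**1. Overall rate, equal sites.** Design effect DE = 1 + (m − 1) × ICC with m = 25. Coverage of an independent-patient 95% interval = 2Φ(1.96/√DE) − 1. Half-width = 1.96 × √(p(1 − p) × DE/N), with N = 1,000 and an assumed p = 30%.

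| Site ICC | DE | Effective N | Coverage | Half-width (points) |
|---|---|---|---|---|
| 0 | 1.00 | 1,000 | 95% | 2.8 |
| 0.01 | 1.24 | 806 | 92% | 3.2 |
| 0.02 | 1.48 | 676 | 89% | 3.5 |
| 0.05 | 2.20 | 455 | 81% | 4.2 |

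**2. Unequal sites.** With coefficient of variation c in site size, DE = 1 + ((c² + 1)m − 1) × ICC. For c = 0.6 and ICC 0.05, DE = 1 + 33 × 0.05 = 2.65 and coverage is 77%. For c = 1.0, DE = 1 + 49 × 0.05 = 3.45 and coverage is 71%.

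**3. Countries.** Let the country ICC be r and the additional site ICC be s, with k sites per country. A site-clustered variance captures about A = 1 + 24(r + s). The true factor is B = A + (k − 1) × 25 × r. Coverage of the site-clustered interval is 2Φ(1.96 × √(A/B)) − 1.
- 15 countries, k = 3, r = 0.01, s = 0.04: A = 2.20, B = 2.70, coverage 92%.
- 12 countries, k = 4, r = 0.03, s = 0.01: A = 1.96, B = 4.21, coverage 82%.

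Simulation over similar inputs gave about 81% to 93% for intervals clustered on site and about 95% for t intervals clustered on country. Clustering on site alone can therefore still be too narrow.

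**4. Mortality among admitted patients.** Section 3.1 says of the pilot: "In hospital mortality rate is about 6 % which is very high for general hospitalized patients". This reads as a rate among admitted patients, though no denominator is given. Assume 25% to 45% are admitted, so 6 to 11 per site and 240 to 550 in all. The half-width at 6% is 2.0 to 3.0 points if patients are independent, 2.2 to 3.2 at ICC 0.02 (DE 1.1 to 1.2) and 2.4 to 3.4 at ICC 0.05 (DE 1.25 to 1.5).

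**5. Planned tests and AUCs.** Simulated size of a nominal 5% Chi-square test (45 sites of 25, outcome 30%, groups 50:50) was 4.9% to 5.1% when the group mix did not vary by site. It was 5.4% to 10.6% with a group-membership ICC of 0.05 to 0.20; the top value also needs an outcome ICC of 0.10. For hospitalization, the overall AUC differed from the within-site AUC by −0.013 to +0.011 around 0.74, against a sampling error of about ±0.03.

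**6. Mortality population.**

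| Place | Patients covered |
|---|---|
| Section 3.2, objective | All those presenting to the ED |
| Synopsis Section 13 | 30-day status, no restriction |
| CRF, Appendix 1 | 30-day status under hospitalized patients |

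The difference is large. If 6% of admitted patients die, that is 0.06 × 0.25 = 1.5% to 0.06 × 0.45 = 2.7% of all attenders, before ED deaths and later deaths among those sent home.

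**The case against.** The best defence is that the study calls itself descriptive and enrols every consecutive patient, so counts and medians correctly describe the patients enrolled. The reduced coverage belongs to an interval that nobody has planned, and no planned result is shown to be wrong. That is true. But the objectives claim more than a description of those enrolled: they name patients across Europe, and Section 11.1 plans significance tests. Estimates with that aim need a stated precision.

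A second defence is that coordinators choose the sites, so no interval supports a statement about Europe. This stands as a limit on interpretation. A clustered interval still shows how far the result depends on which EDs and countries took part.

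Two stronger readings are tempting. One is that the planned tests and AUCs are invalid because they treat patients as independent. Steps 4 and 5 do not bear this out: the effect on mortality is modest, and that on tests and AUCs is small unless group mix differs strongly by site. The other is that the plan leaves the mortality population undefined, so that a sentence in Section 11.1 would settle it. In fact Section 3.2 names the population; the conflict is with what the CRF collects, and an analysis sentence cannot supply 30-day status for discharged patients.

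**Conclusion.** The point holds as a worthwhile and inexpensive improvement in reporting; it does not invalidate the design. That no interval is planned, and that site and country are unused, can be read directly from Section 11.1. The size rests on assumed ICCs: at 0.01 to 0.05 and 25 patients per site, an independent-patient interval for an overall rate covers about 92% to 81%, and less with unequal sites or differences between countries. The direction is clear for overall rates; the amount is not known.

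The 30-day mismatch between objective and CRF rests on no ICC and needs to be resolved whatever is decided about intervals.

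**What to change.** 1. In Section 11.1, report the main proportions, medians and AUCs with 95% intervals that allow for clustering. Cluster on country, with EDs nested within it, where there are enough countries, using a small-sample t method or a bootstrap that resamples countries. Otherwise cluster on site. The CRF already carries both codes.
2. Keep the planned patient-level tests. Add a cluster-robust check only where the group mix differs strongly between sites.
3. Reconcile Section 3.2 and synopsis Section 13 with the CRF: either record 30-day status for all attenders, or restrict the stated 30-day rate to hospitalized patients. Say whether ED deaths count in in-hospital mortality.
4. State in the report that sites were chosen by national coordinators, so the intervals do not make the estimates representative of Europe.

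The cost is usually wider intervals and some analysis time, plus follow-up of discharged patients if that option in item 3 is taken. Under Section 10.3.1 protocol changes need steering-committee acceptance and local ethics approval, and under Section 10.3.2 none is accepted during recruitment. Extending the CRF would therefore have to be settled before recruitment starts.

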13. OUTCOME VARIABLE

Length of stay in the ED and Length of stay in the hospital if hospitalized.

Status at 30 days: alive or dead.

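### Hospital length of stay is analysed as a complete measurement although the CRF allows open stays and deaths in hospital; no rule says how either is handled, so stays may be understated, probably most in high-score groups

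*Combined protocol and SAP*

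**What the plan says.** The outcome section of the synopsis (item 13) names "Length of stay in the ED and Length of stay in the hospital if hospitalized", and adds "Status at 30 days: alive or dead".

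Section 11.1 sets one method for all continuous variables: medians with interquartile ranges, then "The inter-group differences between the continuous variables will be evaluated using the Kruskal-Wallis test and the Mann-Whitney U test", with Bonferroni correction. Length of stay gets no exception. The groups are set out in the same section: "Patients will be classified based on their ages, emergency medicine diagnosis and early warning scores".

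The CRF (Appendix 1) asks for total days in hospital, in wards and in ICU. Beside these fields is a box labelled "Still in Wards" and a matching one for the ICU. Neither carries a date. A further box reads "Death during Hospitalization", with no date of death.

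No section says what length is entered for a patient who has not left, on what day that is judged, or whether stays ended by death are pooled with stays ended by discharge. Section 11.2 (Missing data) is one sentence and does not touch this.

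**The concern.** An open stay is right-censored: only a lower bound is known. A median or rank test needs a value for it, so in practice it is either left blank and dropped or entered as if finished. Dropping removes the longest stays. A stay ended by death is a complete number of days, but pooled with discharges an early death ranks as a short stay, which reads as a good result.

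Neither effect need be equal across the groups compared. Section 3.1 reports that in the pilot all three scores were higher in non-survivors and in ICU patients. Deaths, and plausibly long stays, should therefore gather in the high-score classes. What is at stake is whether the registry describes the hospital stay of its sicker patients correctly, and whether the difference from less sick patients is blunted.

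**Working it through.** The plan states no length-of-stay figure to reproduce. The check asks how far the planned median moves under each way of handling open stays and deaths.

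**Inputs from the documents (Section 3.1).** In-hospital mortality in the pilot: "In hospital mortality rate is about 6 % which is very high for general hospitalized patients". ICU share of hospitalised older patients: 30%.

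**Assumptions (not in the documents).** Time to live discharge is log-normal with median *m*. A proportion *p* die in hospital, with log-normal time to death of median *d*. The log-scale SD is 0.9 for both. Stays beyond day 30 are open. The pilot's 70/30 split is used only to choose *p* for a less sick and a sicker group:
- 0.7 × 3% + 0.3 × 13% = 6.0%
- 0.7 × 2.1% + 0.3 × 15% = 5.97%

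**Formulas.**
- Distribution of actual stays: F(x) = (1 − p)·Φ(ln(x/m)/0.9) + p·Φ(ln(x/d)/0.9)
- Open share: 1 − F(30)
- Median of actual stays: F(x) = 0.5
- Median with open stays dropped: F(x) = 0.5·F(30)
- Median with open stays kept at day 30: again F(x) = 0.5, as long as fewer than half are open
- Median time to live discharge, the dead never being discharged: (1 − p)·Φ(ln(x/m)/0.9) = 0.5

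**Step 1: open stays, with d = 4 days.**
- Less sick, m = 6, p = 3%: F(30) = 0.97 × 0.963 + 0.03 × 0.987 = 0.964.
- Sicker, m = 10, p = 13%: F(30) = 0.87 × 0.889 + 0.13 × 0.987 = 0.902.

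| Group | m | p | Open | Median, kept at day 30 | Median, dropped | Fall |
|---|---|---|---|---|---|---|
| Less sick | 6 | 3% | 3.6% | 5.9 | 5.7 | 0.2 |
| Less sick, longer stays | 8 | 2.1% | 7.0% | 7.9 | 7.3 | 0.6 |
| Sicker | 10 | 13% | 9.8% | 9.0 | 8.0 | 1.0 |
| Sicker, longer stays | 14 | 15% | 17.1% | 12.0 | 9.7 | 2.3 |

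Dropping understates the median in every row, and more in the sicker groups. Keeping open stays at day 30 gives the same median as the actual stays.

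**Step 2: rank test.** This was simulated with 300 hospitalised patients (assumed; the documents give no number), 30% of them in the sicker group, m = 6 versus 10, p = 3% versus 13%, d = 4 and two-sided 0.05 (assumed). Power is 0.92 with complete stays, 0.92 with open stays kept at day 30 and 0.81 with open stays dropped.

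**Step 3: deaths counted as completed stays.** The comparison is with the assumed live-discharge medians of 6 and 10 days, using p = 3% and 13%.
- *d* = 3 to 5 days: 5.9 to 6.0 in the less sick group, 8.8 to 9.2 in the sicker group.
- *d* = 10 days: the sicker group shows no shift (10.0).
- *d* = 20 days: the sicker group rises to 10.9.
- *p* = 30% and *d* = 4 in the sicker group: its median is 7.7, and the rank-test power of step 2 falls from 0.92 to 0.54.

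**Step 4: what the alternative would report.** With death as a competing event, the median time to live discharge is 6.2 days (m = 6, p = 3%) and 11.8 days (m = 10, p = 13%). The proportion discharged alive by day 30 is 0.97 × 0.963 = 0.93 and 0.87 × 0.889 = 0.77. All four figures lie within 30 days of follow-up.

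**The case against.** The strongest reply is that the plan never says open stays are dropped. If they are entered at a common day 30, the medians and the rank-test power do not change. This stands, and it is why understatement is conditional. But no section tells sites to do so. Section 5.6 asks for complete forms and Section 11.2 accepts a form only if certain unnamed variables are present, so a blank field leading to exclusion is plausible.

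Second, a stay ended by death is a true value if length of stay means bed use. This also stands. A reader might take the whole distance between the planned summary and time to live discharge as bias; the documents do not support that. In the longest scenario (m = 14), the dropped-stay median is 9.7, the actual-stay median 12.0 and the live-discharge median 17.1 days. Only 12.0 − 9.7 = 2.3 days is error in measuring the stay. The other 17.1 − 12.0 = 5.1 days comes from changing the target. The protocol does not say which target it means.

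Third, a reader might infer that the plan will show the sickest patients staying no longer than others. That would need a mortality far above the only documented figure, about 6%. Nor does Section 11.1 name a ward-versus-ICU comparison of stay; its groups are age, diagnosis and score.

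Finally, length of stay appears in no listed objective, and the endpoints of the ROC analysis are hospitalisation and in-hospital mortality. The main objective is unaffected. Stay is still a declared outcome, and the remedy is cheap.

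**Conclusion.** The gap is real. A declared outcome that can be censored or ended by death is assigned methods for complete values, with no handling rule. If open stays are dropped, the illustrative loss in the median is about 0.2 to 0.6 days in less sick groups and about 1 to 2.3 days in sicker groups. If they are kept at a common day 30, the loss is nil. Early deaths shorten the pooled median further in sicker groups, while late deaths leave it unchanged or lengthen it.

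These sizes rest on assumed log-normal stays, an assumed time to death and a mortality split chosen to match the pilot's 6%. The documents give neither the share of open stays nor the timing of deaths. That understatement falls most on high-score groups is therefore the probable direction, not something that follows from medians and rank tests as such. The plan should be changed, but the point does not threaten the main objective.

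**What to change.** Add to Section 11.1:

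1. State whether length of stay means bed use, time to live discharge, or both.
2. Judge open stays at a fixed day 30, the CRF's existing status time point, from a stated origin. Keep them as censored at that day and never drop them.
3. Report the number of open stays and in-hospital deaths in each group.
4. Analyse time to live discharge up to day 30 with in-hospital death as a competing event (Aalen-Johansen cumulative incidence, Gray's test) across the age, diagnosis and score groups. At minimum, report stay separately for survivors and non-survivors.
5. Keep the crude median and interquartile range as a description of bed use.

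The CRF is close to sufficient but not fully so. The open-stay boxes need a judging date. As there is no date of death, sites must be told to complete total hospital days for patients who die.

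The cost is a few lines of text, a CRF instruction and a little more analysis. The downside is a summary less familiar to readers than a median.

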10. STUDY OBJETIVE

Principle Objective: Description of Epidemiologic and Age Related Characteristic of geriatric patients presenting to the ED

Secondary Objective: Determination of the prognostic and predictive values of vital sign based triage scores (REMS, MEWS and VIEWS Scores) regarding hospitalization, ICU admission and in-hospital mortality for geriatric patients presenting to ED

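### ICU admission is a named outcome for the three scores but has no ROC, cut-off or accuracy analysis, and the choice of best score has no planned interval or paired comparison

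*Combined protocol and SAP*

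**What the plan says.** Item 10 of the protocol summary sets the secondary objective for the scores ("REMS, MEWS and VIEWS Scores) regarding hospitalization, ICU admission and in-hospital mortality for geriatric patients presenting to ED"). Section 3.2 repeats the three outcomes and adds a choice between the scores: to "determine most suitable Geriatric Emergency Medicine Risk Score regarding hospitalization, ICU admission and in-hospital mortality".

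Section 11.1 then plans three steps:

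- **ROC analysis:** "The predictive power of the scores for hospitalization and mortality in hospital will be evaluated using the Receiver Operating Characteristic (ROC) analysis".
- **Youden cut-offs:** "The optimum cut-off points of the scores will be determined for both of the main endpoints".
- **Sensitivity, specificity, predictive values and likelihood ratios:** "the values of both the scores will be calculated for both hospitalization and mortality at the hospital".

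On the AUCs it says only that their values will be evaluated. It also plans Kruskal-Wallis and Bonferroni-corrected Mann-Whitney tests for continuous variables, without naming the groups.

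The case report form (Appendix 1) has a box "Admitted to Intensive Care Unit" and fields for "Total Length of Stay in Wards" and "Total Length of Stay in ICU".

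**The concern.** The objectives list three outcomes and the predictive analysis covers two. ICU admission drops out of the ROC, cut-off and accuracy steps alike, so it cannot enter the choice of score on the same footing as hospital admission and death in hospital.

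The second issue is how the choice would be made. Naming one score as best suited is a comparative claim. The plan would rest it on AUCs and accuracy measures with no stated uncertainty, and it ignores that the three scores are measured on the same patients and are therefore paired. If the true differences are small, the ranking could be chance, mainly for death and ICU admission and less so for hospital admission.

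**Working it through.** **Objectives against analysis**

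| Outcome | Item 10 and section 3.2 | ROC | Cut-off | Accuracy | On the CRF |
|---|---|---|---|---|---|
| Hospital admission | yes | yes | yes | yes | yes |
| ICU admission | yes | no | no | no | yes |
| Death in hospital | yes | yes | yes | yes | yes |

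No other section fills the gap. This part needs no assumption.

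**Precision of the planned comparison.** The plan gives no figure to reproduce, since section 11.3.1 states that no formal sample size was calculated. The inputs are:

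- From section 11.3.1: 40 to 50 sites with an average of at least 25 patients, so 40 × 25 = 1,000 to 50 × 25 = 1,250 as a minimum.
- From the pilot findings in section 3.1: 30% of hospitalised patients went to ICU, and in-hospital mortality was about 6% (denominator unclear).
- Assumed, not in the documents: 30% to 50% hospitalised, AUC 0.75 to 0.80, sensitivity 70% to 80%, independent patients.

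Event counts:

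- Hospital admissions: 0.30 × 1,000 = 300 to 0.50 × 1,250 = 625.
- ICU admissions: 0.30 × 300 = 90 to 0.30 × 625 ≈ 188.
- Deaths: 0.06 × 1,000 = 60 to 0.06 × 1,250 = 75 if the 6% applies to all presenters; 0.06 × 300 = 18 to 0.06 × 625 ≈ 38 if it applies to hospitalised patients.

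*AUC (Hanley-McNeil), m events and n non-events.* With P1 = A/(2 − A) and P2 = 2A²/(1 + A),

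Var = [A(1 − A) + (m − 1)(P1 − A²) + (n − 1)(P2 − A²)]/(mn).

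For ICU admission with A = 0.75, m = 90, n = 910: P1 = 0.600, P2 = 0.6429, A² = 0.5625. Var = (0.1875 + 89 × 0.0375 + 909 × 0.0804)/81,900 ≈ 0.000935, so SE ≈ 0.0306 and the half-width is 1.96 × 0.0306 ≈ 0.060.

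*Sensitivity (Wilson), cut-off treated as fixed.* Half-width = z√[p(1 − p)/n + z²/(4n²)]/(1 + z²/n), where n is the number of events. For p = 0.80 and n = 90 this is 0.082.

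*Paired AUC difference.* 1.96 × the empirical SD over 1,200 simulated studies per setting, using two discretised correlated normal scores with correlation 0.3, 0.6 or 0.8 (assumed) and true AUCs of 0.80 v 0.78 or 0.72 v 0.70.

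| Outcome | Events | AUC half-width | Sensitivity half-width | Paired-difference half-width |
|---|---|---|---|---|
| Hospital admission | 300–625 | 0.025–0.035 | 0.03–0.05 | 0.017–0.042 |
| ICU, among all presenters | 90–188 | 0.039–0.060 | 0.06–0.09 | 0.025–0.066 |
| ICU, among admitted | 90–188 | 0.041–0.064 | 0.06–0.09 | 0.026–0.076 |
| Death, 6% of presenters | 60–75 | 0.061–0.073 | 0.09–0.11 | 0.036–0.081 |
| Death, 6% of hospitalised | 18–38 | 0.086–0.133 | 0.12–0.20 | 0.050–0.143 |

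The 0.72 v 0.70 pair sets the upper ends of the last column. With 0.80 v 0.78 alone they are about 0.067 for ICU admission and 0.13 for death.

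With true AUCs of 0.80 and 0.78, ranking on point estimates puts the worse score first in about 3–15% of simulated studies with 300 hospital admissions, 13–24% with 90 ICU admissions, 17–31% with 60 deaths and 32–38% with 18 deaths.

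**Site clustering.** In simulations with 40 unequal sites, the AUC half-width changed by a factor of 0.96 to 1.09 at an assumed ICC of 0.05–0.10, and 0.97 to 1.35 at 0.20.

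**ICU denominator.** With normal scores, discharged patients at mean 0, ward patients shifted by 0.3 to 0.8 SD and ICU patients by 0.8 to 1.3 SD (all assumed), the AUC among all presenters exceeded that among admitted patients by 0.036 to 0.157 whenever the ICU shift was larger than the ward shift. The denominator therefore has to be stated.

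**The case against.** **The group tests may already cover ICU admission.** The pilot compared the scores between ICU, ward and discharged patients, and the Kruskal-Wallis and Mann-Whitney plan could repeat this. The Mann-Whitney U divided by the product of the two group sizes is the AUC, so discrimination would nearly be supplied. This stands in part. But section 11.1 names no groups, and a group test yields no cut-off, sensitivity, specificity, predictive value or likelihood ratio, which the other two outcomes do get.

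**The omission may be carried-over wording.** Section 11.1 reads in places like a finished report, and its two-score phrasing does not fit three scores. That is plausible, and the references to both scores and both endpoints are probably slips. The text still needs correcting, because an analyst who follows it produces no ICU accuracy result.

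**The study is descriptive, and intervals are not excluded.** True, and no power calculation or hypothesis test is asked for. But choosing a score is comparative, and intervals are ordinary descriptive reporting.

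**The precision figures rest on assumed inputs.** They do. With 20–50% hospitalised and an AUC of 0.70, ICU admissions would number 60 to 188 and the half-width would be 0.044 to 0.076. Twenty-five per site is a minimum, so larger enrolment narrows every interval. The ICU omission depends on none of this.

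**The analysis could be added later.** The data will exist, but it would then not be pre-specified.

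**Conclusion.** The concern holds. The main defect is that 1 of 3 named outcomes has no predictive-accuracy analysis, which follows from the text alone. The missing intervals and paired comparison are a supporting point: at the expected minimum enrolment, and on the assumptions above, the half-width of a paired AUC difference for ICU admission or death often exceeds a true difference of 0.02 by a wide margin, so chance could settle the ranking. For hospital admission the risk is smaller. The main epidemiological objective is not affected. The plan should be changed, but the study does not fail without the change.

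**What to change.** In section 11.1:

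1. Add ICU admission to the ROC, cut-off and accuracy analyses. Define the event as the ticked box on the case report form. The box carries no timing and the form gives only total ward and ICU days, so direct admission and later transfer may not be separable in patients who had both. State the denominator; all presenters fits the wording of summary item 10.
2. Report each AUC with a 95% confidence interval and, for each outcome, the paired AUC differences between the three scores with 95% confidence intervals (DeLong, or a bootstrap that resamples sites). That is 3 pairs × 3 outcomes = 9 differences, so say whether the intervals are adjusted for multiplicity. Base any statement about the best score on these together with the planned accuracy measures, and allow the conclusion that the scores cannot be told apart.
3. Correct the wording so that it names REMS, MEWS and VIEWS and all three outcomes.

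The cost is plan text and a few lines of code, with no new field on the form. Separating direct ICU admission from later transfer would need a new field and is not asked for. Section 10.3.1 requires steering committee acceptance and local ethics approval for a protocol change, and section 10.3.2 bars changes during recruitment, so the change should be made outside that window and before results are seen. The downside is a little more analysis and the possibility that no clear best score emerges.
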